4. OBJECTIVES*

Surgery is a life-saving procedure for patients with cancer and can enhance quality of life for patients with intractable abdominal or thoracic disease. Although most patients tolerate the procedure well, frail older adults have as much as a threefold increase in the risk of adverse outcomes after surgery.¹ In response to this risk, some investigators^{2,4} have studied preoperative exercise interventions (a.k.a. pre-habilitation).

So far, pre-habilitation studies^{2,4} have shown improvement in endurance but not a reduction in adverse outcomes such as medical complications, discharge to nursing home, or readmission. Potential explanations are that these studies were too small to show a difference but also they did not focus on frail older adults who could benefit most from prehabilitation. A final explanation is that they relied on clinic visits with physical therapists or kinesiologists which can add to the stress and cost of surgery for patients already burdened with appointments in the short preoperative period.

A home walking prescription self-monitored with a modern pedometer (e.g. Fitbit type wristband) provides a convenient and cost-effective method for prehabilitation. Despite the apparent advantages of a home walking program, no one has demonstrated that such a program can reduce the incidence of adverse outcomes or improve physical status assessments such as endurance, balance, gait speed, strength, and self-reported function. If our investigative group establishes that a walking prescription supported by pedometer improves these assessments, we would be in a favorable position to embark on a larger study to demonstrate a reduction in adverse clinical outcomes.

There are other data that would be helpful to collect prior to embarking on the larger study. These include the role of varying duration of the walking regimen. Given the rush to proceed with surgery in anxious patients, it would be important to know how well the intervention works over the range of times available and if there exists a threshold of duration (e.g. 1-2 weeks) below which a walking prescription would have no effect.

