Additionally, it would be important to analyze step counts from the pedometer and the percentage of days in which individual patients achieved prescribed targets. This would permit assessing whether any improvements in physical status resulted from the walking intervention. Conversely, if there is no improvement in physical status assessments, we could diagnose if nonadherence with the walking prescription was the reason. Finally, it would be helpful in guiding future research to calculate the time and cost required to recruit eligible patients as well as to assess patient satisfaction with the walking prescription.

INVESTIGATOR STUDY PLAN - REQUIRED

We therefore propose a study of 400 older adults scheduled for surgery with the following aims which will prepare us to conduct a larger trial focused on clinical outcomes.

Aim 1: To assess the impact of a walking prescription intervention on outcomes of endurance, balance, gait speed, strength, and self-reported function in patients with frailty.

Aim 1a: To estimate improvement in outcomes as a function of duration of the walking intervention.

Aim 1b: To re-estimate the effect of the intervention adjusting for the percentage of days each patient met his/her walking goal.

Aim 1c: To measure patient satisfaction with the walking intervention.

Aim 2: To measure the average time and cost required to recruit and follow up each patient.

Aim 3: Postoperative outcomes: we may also measure several postoperative outcomes

Change in six-minute walk distance from baseline

The number of steps per day in the hospital

Time to 100 steps at the day of discharge.

Discharge to skilled nursing facility

Length of stay

Thirty-day outcomes including serious complication, readmission, and death

Aim 4: Measure the performance of Edmonton frailty score for predicting 30 day outcomes including serious complication, readmission, death.

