5. BACKGROUND*

Frail older adults are at elevated risk for adverse postoperative outcomes. With aging, impairments underlying physical function emerge, such as muscular weakness, decreased lower extremity proprioception/balance, and visual deficits. These impairments limit walking ability which in-turn limits participation in daily life activities. A more sedentary lifestyle ensues leading to further lower extremity weakness which becomes manifest in slow gait speed.⁵ These sedentary individuals also undergo significant loss of endurance/exercise capacity as their bodies becomes less efficient at using oxygen.⁶ This is significant given the stress on the body during surgery. Frail older adults are also at risk for delayed mobilization which can lead to multiple other medical complications. Afilalo et al.¹ found that cardiac surgery patients with slow gait speed, a good single marker of frailty, had more than a threefold increase in morbidity and mortality (odds ratio= 3.05 95% CI 1.23-7.54)

In that study, the authors used gait speed < 0.83 m/s which is a relatively stringent criterion for slow speed. Using a more liberal gait speed criterion (≤ 1.0 m/s), our research group still found a 1.7 fold increased risk (hazard ratio=1.71 95% CI 0.67-4.31) of developing an adverse postoperative course for older adults.⁷

A pure walking intervention (without resistance or other exercise components) can lead to improved physical status in frail older adults but it has not been tested previously in the surgical setting. Investigators have shown that long term care residents (typically frail) can participate and benefit from regular walking.⁸ Similarly, investigators with the COPD Seat study⁹ have

INVESTIGATOR STUDY PLAN - REQUIRED

proposed looking at whether a two-week movement intervention (i.e. essentially a walking program) titrated to step count can improve balance, gait speed, and strength in patients discharged after hospitalization for COPD.

Our proposal will assess the role of a walking intervention in the surgical context assessed over multiple dimensions of physical status-endurance, balance, gait speed, strength, and self-reported function.

The gains we achieve with the walking intervention will pay dividends in terms of clinical endpoints. We hypothesize that a preoperative walking intervention will lead to improvement in physical status by the time of surgery.

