9. STUDY TIMELINES*

The overall study timeline is two years from start of recruitment. The first year will focus on preparation (training on frailty measurement, scripting interviews, and testing the questions we ask) and recruitment of study subjects. Individual subjects will be actively involved for 30 minutes during their first appointment (not including time spent in clinic appointment), approximately 15 minutes during the day of their surgery, and potentially approximately ten additional minutes on their day of discharge from the hospital, though patient data collection will continue for up to one year after the day of surgery.

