10. STUDY ENDPOINTS*

Aim 1a: Endurance: For endurance, we will measure 6MWD following the American Thoracic Society (ATS) guideline.¹⁵ Briefly, we will establish an unimpeded 20m course within the colorectal surgery office. Studies have varied with the length of course but a multicenter study mentioned in the guideline statement¹⁵ suggested lengths ranging from 20 to 50m did not significantly change patient walking distance results. Every effort will be made to control for variation, including the amount of encouragement provided by project staff member and stopping conditions. We will follow the ATS guideline providing encouragement at one minute intervals.

Patients may stop by leaning against the wall before resuming. At the end of six minutes, we

INVESTIGATOR STUDY PLAN - REQUIRED

will record patient-perceived exertion using the Borg scale. We will also ask the patient for a reason for stopping. Recording the perceived exertion and reason for stopping will allow us to interpret outlier values and other potential variation among patients who otherwise have similar predicted walk distance. Although a research staff member will record the walk distance, we will require that a RN or another more senior clinician be present during the examination to monitor for patient fatigue or angina. Reasons for immediately stopping a 6MWD include the following:(1) chest pain, (2) intolerable dyspnea, (3) leg cramps, (4) staggering, (5) diaphoresis, and (6) pale or ashen appearance. If space is not available, we will conduct the test on a treadmill with guard rails which should provide adequate safety. An RN or another more senior clinician will be present during the examination to monitor for patient fatigue or angina for subjects completing the assessment on a treadmill as well.

Aim 1a: Balance, strength and gait speed: We will follow the short performance physical battery (SPPB) protocol by Guralnik.¹¹ A research staff member will measure the patient's ability to balance in three separate positions: side-by-side stand, semi-tandem stand, and tandem stand. Scores range from 0 for someone unable to balance in any of the positions to 4 for someone able to stand in each position for 10 seconds. Given we have already measured gait speed during the screening process we will move on to patient's ability to perform five chair sit-to-stand maneuvers with scoring based on the time required.

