Aim 1a: Self-reported function: We will administer the 12 items of the Veteran Rand (VR-12) in order to measure self-reported function.¹⁶ We will then calculate the summary physical component score (PCS) using a published algorithm.¹⁶ The algorithm norms PCS to range between 0 and 100, with 50 as a mean, and 10 as the standard deviation for the US population.

Aim 1b: Adherence with exercise: We will measure the percentage of days in which the participant meets his/her step count target for intervention patients and activity journals for both groups of patients

Aim 1b: Patient satisfaction: We will design a custom instrument to assess patient satisfaction with our intervention.

Aim 2: Time and cost to recruit 400 frail older adults: We will calculate the time and cost to recruit 400 patients. We will assess time in multiple ways: number of calendar days and number of working clinic days. For cost, we will assign an hourly wage for research staff member and RN efforts and then multiply by the number of hours required to perform recruitment, follow-up telephone calls, and follow-up assessments.

Aim 3: Postoperative outcomes: we may also measure several postoperative outcomes, including:

Change in six-minute walk distance from baseline

The number of steps per day in the hospital

Time to 100 steps at the day of discharge.

Discharge to skilled nursing facility

INVESTIGATOR STUDY PLAN - REQUIRED

Length of stay

Postoperative Recovery (measured via quality of recovery scale, abdominal surgery impact scale)

Thirty-day outcomes including serious complication, readmission, and death

Aim 4: Thirty-day outcomes including serious complication, readmission, and death

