Participants may walk steps over the course of a day or in one session. The initial walking prescription will also provide instructions to the participant to increase his/her number of steps each week by 10 to 20%.

A research staff member will then orient the participant to the pedometer

Weekly calls: During the interim between the day of consultation until the day of surgery, a study staff member will make weekly calls to each patient. The calls will provide participants an opportunity to report any symptoms which could warrant stopping the walking regimen and/or seeking urgent medical attention. In addition, we will train the study staff member to troubleshoot any problems setting step count targets or other problems with the pedometer. In cases in which the pedometer fails, we will budget to have additional pedometers available to mail to the patient.

Activity log: we will ask participants to log all of their physical activities-date, activity type, number of minutes. We will submit a copy of the activity log to the irb for approval prior to recruiting randomized participants to complete it.

Control subjects: a study staff member will provide general walking advice with typical warnings about when to stop (e.g., chest pain, breathing difficulty, or fall). Control subjects will receive no other intervention. We will also ask control subjects to log their physical activities.

Preoperative assessment: On the day of preoperative testing, which will usually occur three to five weeks after the baseline measurement, a research staff member or other project staff member will collect the pedometer and record the repeat physical status assessments (6MWD and SPPB). On the day of surgery, we may also place a research grade monitor on patients so as to track their steps while in the hospital.

Hospital period assessment: By the day of discharge, we will collect the research grade monitors and repeat our physical status measurements.

INVESTIGATOR STUDY PLAN - REQUIRED

In order to test the above procedures in the randomized individuals, we will enroll up to 15 patients as test patients. All these patients will undergo screening, baseline assessment/interview, follow-up assessment on day of preoperative testing, in-hospital step tracking and Hospital period assessment.

30 day assessment: Approximately 30 days from day of surgery, at office of surgery clinic, we will repeat our physical status measurements

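### The preoperative assessment lists only the 6MWD and SPPB, so self-reported function (VR-12), one of the five Aim 1 change outcomes, has no named repeat before surgery

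*Combined protocol and SAP*

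**What the plan says.** Section 4 sets Aim 1 as the effect of the walking prescription on "outcomes of endurance, balance, gait speed, strength, and self-reported function in patients with frailty". Section 10 gives one instrument for the last of these: "We will administer the 12 items of the Veteran Rand (VR-12) in order to measure self-reported function".

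Section 5 fixes the time frame: "We hypothesize that a preoperative walking intervention will lead to improvement in physical status by the time of surgery". It also counts self-reported function as part of physical status, describing "multiple dimensions of physical status-endurance, balance, gait speed, strength, and self-reported function".

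Section 11 names three instruments at baseline: 6MWD, SPPB and VR-12. At the preoperative assessment, usually three to five weeks later, staff are to "collect the pedometer and record the repeat physical status assessments (6MWD and SPPB". The discharge and 30-day assessments repeat the physical status measurements without an itemised list. The VR-12 is next named at the 6-month contact, where attempts run over months 7 and 8.

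Section 13 analyses within-participant change in five physical status measures (Aim 1), builds five Aim 1c models, one per measure, and compares all five with the MCID after each batch of 10 patients.

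**The concern.** The analysis needs a change score for self-reported function over the period in which patients walk, and the visit schedule does not clearly provide the second measurement. Staff who build the preoperative form from the two-item list will not collect the VR-12. Self-reported function would then drop out of Aims 1, 1a and 1b, one of the five Aim 1c models, and the batch reviews.

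Later VR-12 values cannot stand in. Discharge, 30 days and 6 months all follow the operation, so a change to any of those points mixes the effect of surgery and recovery with that of preoperative walking. The loss is permanent for each patient, because a preoperative value cannot be collected after surgery.

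**Working it through.** The plan states no figure to reproduce. The check sets the visit schedule against the analysis.

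**Step 1. Which visit Aim 1 change refers to.** Section 13 does not say, so this is an inference. Section 5 places the improvement before surgery. Aim 1a relates change to the time available for the intervention. Aim 1b uses the 30 days held in pedometer memory, and Section 11 has the pedometer collected at the preoperative assessment. All three point to that assessment.

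**Step 2. Instruments named at each assessment.**

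| Assessment | Instruments named | Before surgery? |
|---|---|---|
| Baseline (Section 11) | 6MWD, SPPB, VR-12 | yes |
| Preoperative testing day (Section 11) | 6MWD, SPPB | yes |
| Day of surgery (Section 11, sentence on clinician presence) | 6MWD | not stated |
| Discharge (Section 11) | 6MWD; rest not named | no |
| 30 days (Section 11) | 6MWD; rest not named | no |
| 6-month contact (Section 11) | VR-12 | no |

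The VR-12 is named twice: at baseline and after surgery. It is not named between the two.

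**Step 3. The five outcomes at the preoperative repeat.**

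- Endurance (6MWD), balance and strength (SPPB): clearly named, 3.
- Gait speed: unclear, 1. It belongs to the SPPB, but Section 10 passes over it: "Given we have already measured gait speed during the screening process we will move on to" the chair stands. The screening text in Section 11 describes the Edmonton scale and names no gait speed test.
- Self-reported function (VR-12): not named, 1.

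3 + 1 + 1 = 5. If naming the SPPB is taken to cover gait speed, the count is 4 named and 1 not named. The VR-12 result is the same either way.

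**Step 4. Which day the assessment falls on.** Section 11 puts it on the day of preoperative testing. The later sentence on clinician presence lists the 6MWD at baseline, day of surgery, hospital period and 30 days, and omits the preoperative testing day. Section 9 allots "approximately 15 minutes during the day of their surgery" and lists no preoperative testing visit. None of these passages names the VR-12.

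**Step 5. Cost of adding the VR-12.** The documents give no completion time, so 2 to 5 minutes is assumed. Section 24 gives 200 patients and Section 25 gives 400.

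- Low: 200 × 2 / 60 = 6.7 hours.
- High: 400 × 5 / 60 = 33.3 hours.

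**The case against.** The strongest reply is that this is an incomplete parenthesis and no measure has been dropped. The baseline paragraph uses the term physical status assessments for a set that includes the VR-12. Section 4 speaks of a program that could "improve physical status assessments such as endurance, balance, gait speed, strength, and self-reported function", and Section 13 says five throughout. On that reading, repeating the assessments already means repeating the VR-12. This is a fair reading and cannot be excluded. But where the protocol clearly wants the VR-12, at baseline and at 6 months, it names it; at the preoperative assessment it lists two instruments and leaves out the third. If the VR-12 is intended, the list is wrong. If it is not, the count of five in Section 13 is wrong. One of them has to change.

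A second reply is that the consequence is limited, and much of this stands. One outcome of five is affected and none is designated primary. The batch reviews can run on the other measures, since their goal is to exceed the MCID on one or more. Section 11 requires IRB review of the data collection tools before use and allows up to 15 test patients to try the procedures. The VR-12 is marked as an attachment that is not available here and might show when it is given.

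The side points are weaker than the main one. Skipping gait speed because it was just measured at screening makes sense at baseline and need not apply weeks later. The test-patient paragraph also places the follow-up on the preoperative testing day, and the 15 minutes on the day of surgery may be for another task, such as placing the step monitor. Neither affects the VR-12 conclusion.

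**Conclusion.** The concern holds: the plan is wrong as written and should be fixed. One of the five Aim 1 outcomes, self-reported function, has no named preoperative repeat although the analysis requires its change. A second, gait speed, is unclear. In Aim 1c, 1 of 5 models would lack its change value.

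This is a count of outcomes; no bias or loss of power has been estimated. It rests on two assumptions: that staff treat the two-item list as complete, and that Aim 1 change runs from baseline to the preoperative assessment, which Section 13 implies but does not state. Confidence is medium for those reasons. That no section names the VR-12 between baseline and surgery depends on neither.

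**What to change.** The essential changes are two:

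1. In Section 11, add the VR-12 to the preoperative assessment for both arms.
2. In Section 13, define Aim 1 change as the preoperative value minus the baseline value for all five measures, and keep the 6-month VR-12 as a recovery outcome.

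If the VR-12 was left out before surgery on purpose, say so and change the count of five in Section 13 to the measures that are repeated.

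In the same edit, name the instruments at the discharge and 30-day assessments. Reconcile Sections 9 and 11 on whether the preoperative assessment falls on the testing day or the day of surgery. Reconcile Sections 10 and 11 so that gait speed is clearly measured at baseline and repeated.

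The cost is one 12-item form, already used at baseline, at an assessment already planned: about 7 to 33 staff hours in total under the assumed 2 to 5 minutes per patient. The participant time statement in Section 9 should be updated too. Section 11 leaves the data collection forms to be written as an early task, so the gap can be closed before randomised data are collected.

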12. DATA AND SPECIMEN BANKING*

No specimens are being collected as part of the research. Data will not be banked for use in future research outside of the scope of this study.

13. Data Analysis and Management

Analysis As a first step, we will examine the distributions of all variables using histograms and summary statistics for continuous variables, and frequencies for categorical variables. We will consider transformations to enhance normality where continuous variables demonstrate substantial skew or outliers.

Aim 1: We will calculate the distribution of within-participant change for each of the five physical status measures and assess the average and median change against the minimal clinically important difference (MCID) for each assessment, as well as the percentage of patients with a minimal clinically important difference. In cases where a MCID is not available we will decide among our expert advisory team members the threshold values that indicate some important improvement. In our analysis we will also examine the role of baseline assessment on the amount of improvement by using a generalized linear model for the outcome of change in physical status controlling for baseline assessment.

Aim 1a: In this aim, we will examine the association of duration of time available for the intervention with within-participant change in physical status outcomes, using nonparametric locally-weighted scatterplot smoothing (LOESS) regression.¹⁷ We will rerun our generalized linear model controlling for duration of time available for the intervention, transforming the duration variable if indicated by the LOESS plots, e.g., piecewise linear if a threshold effect is seen.

Aim 1b: Similar to Aim 1a analyses, we will examine the association of percentage of days (of the 30 days available in pedometer memory), the step count target was met with within-participant change in physical status outcomes, again using LOESS plots. We will rerun our generalized linear model controlling for the percentage of days in which the patient met their step count target, transforming the percentage of days if indicated by the LOESS plots.

Aim 1c: We will calculate the distribution of patient satisfaction with the intervention, using descriptive statistics, e.g., mean, percentiles, as well as a histogram. Using generalized linear modeling, we will measure patient satisfaction adjusted for changes in physical status. Given the possibility of co-linearity of physical status assessments, we will construct five separate models, one for each of the five physical status assessments.

Aim 2: We will calculate the average time and cost required to recruit each patient by taking the total time and cost divided by the number of patients we eventually enroll (i.e. 200 patients).

INVESTIGATOR STUDY PLAN - REQUIRED

Aim 3: In patients for whom we have recorded postoperative six minute walk distance and step counts, we will calculate change in six minute walk distance from baseline to day of discharge. We will also calculate steps per day and time to first 100 steps. We will calculate the average steps per day using postoperative days 1 and 2 given variation in the start time of surgery for the surgical day and time of transportation availability on the discharge date. For the rare patient leaving the hospital on postoperative day 2, we will only use postoperative day 1. For patients with serious complications requiring ICU stay, we anticipate no steps will be taken and will adjust for this in our analysis. We will measure time to walking at least 100 steps in a single bout, defined as continuous minutes walking at least 1 step/minute following example in the literature. Being able to walk 100 steps in a single bout approximates criteria used to predict successful discharge home from acute hospitalization. We recognize that some patients will not walk 100 steps and so we will adjust for this in our analysis (i.e. we will censor their data in survival analysis).

In terms of the other outcomes, we will compute length of stay in hours from the time of surgery until time of discharge. We will also perform chart review between 30 and 120 days after surgery to tabulate number of patients discharged to nursing home, readmitted at 30 days, dead at 30 days, or having a serious complication of 30 days.

Interim Analyses: Given the possibility that our walking intervention does not improve our physical status measures, we will perform the Aim 1 analysis after recruitment of each batch of 10 patients. More specifically, we will assess the average and median change against the MCID for each of the five measures. If we have not achieved the MCID for any of the measures after any one batch, we will work with our advisors, particularly [name], to revise our intervention (e.g. intensifying the walking regimen) with the goal of improving physical status more than the MCID of one or more measures by the time of the next interim analysis.

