“After the first minute, tell the patient the following (in even tones): “You are doing well. You have 5 minutes to go.” When the timer shows 4 minutes remaining, tell the patient the following: “Keep up the good work. You have 4 minutes to go.” When the timer shows 3 minutes remaining, tell the patient the following: “You are doing well. You are halfway done.” When the timer shows 2 minutes remaining, tell the patient the following: “Keep up the good work. You have only 2 minutes left.” When the timer shows only 1 minute remaining, tell the patient: “You are doing well. You have only 1 minute to go.” Do not use other words of encouragement (or body language to speed up). If the patient stops walking during the test and needs a rest, say this: “You can lean against the wall if you would like; then continue walking whenever you feel able.” Do not stop the timer. If the patient stops before the 6 minutes are up and refuses to continue (or you decide that they should not continue), wheel the chair over for the patient to sit on, discontinue the walk, and note on the worksheet the distance, the time stopped, and the reason for stopping prematurely. When the timer is 15 seconds from completion, say this: “In a moment I’m going to tell you to stop. When I do, just stop right where you are and I will come to you.” When the timer rings (or buzzes), say this: “Stop!” Walk over to the patient. Consider taking the chair if they look exhausted. Mark the spot where they stopped.”

INVESTIGATOR STUDY PLAN - REQUIRED

Randomization: we will randomize patients in a 1:1 fashion into intervention and control groups using a prespecified table generated by our study statistician. More specifically we will use REDCap software to assign a study arm assignment using randomly permuted blocks of sizes 4 and 6.

Intervention patients: intervention patients will receive a walking prescription weekly calls from a study staff member as described below

Walking prescription: A study staff member in consultation with study physician (PI or co-I) will then provide the initial walking prescription based on the participants' baseline performance on the 6MWD following a published example^{12,13} and will focus the participant on walking at a moderate intensity (level of approximately 3 on the modified Borg Perceived Exertional Scale;¹⁴ laminated Borg scales will be distributed to participants).

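### Patients are randomised 1:1 to assess the walking prescription, but Section 13 specifies no between-arm comparison and does not say how control patients are used

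*Combined protocol and SAP*

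**What the plan says.** Section 4 gives Aim 1 as "To assess the impact of a walking prescription intervention on outcomes of endurance, balance, gait speed, strength, and self-reported function" in frail patients. Section 5 adds the hypothesis: "We hypothesize that a preoperative walking intervention will lead to improvement in physical status by the time of surgery". Under Randomization, Section 11 states that "we will randomize patients in a 1:1 fashion into intervention and control groups". Controls are given walking advice and keep an activity log, and receive nothing else.

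Section 13 is the only analysis plan. For Aim 1 it says: "We will calculate the distribution of within-participant change for each of the five physical status measures and assess the average and median change against" an MCID. It adds the percentage of patients reaching the MCID and a "generalized linear model for the outcome of change in physical status controlling for baseline assessment". Aim 1a examines the "association of duration of time available for the intervention with within-participant change in physical status outcomes" by LOESS and then reruns the model with duration. Aim 1b does the same with adherence: "We will rerun our generalized linear model controlling for the percentage of days in which the patient met their step count target". Section 4 describes that last step differently: "To re-estimate the effect of the intervention adjusting for the percentage of days each patient met his/her walking goal".

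Outside Section 13, Section 10 says exercise self-efficacy is collected so that baseline differences between intervention and control patients can be allowed for when efficacy is interpreted.

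**The concern.** The aim and the hypothesis are about the effect of an intervention, and the design randomises patients so that this effect can be separated from everything else that happens between two tests. Repeat testing, general advice, keeping a log and the natural course before surgery can all move the six-minute walk distance (6MWD) and the short physical performance battery (SPPB). The control arm shows how far. Section 13 does not say that this information enters the analysis.

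Followed literally, the plan reports whether patients changed by an MCID. It does not report whether the prescription changed them. Section 4 says that establishing improvement would put the group in a position to start a larger trial, so the result feeds a real decision. If the contrast is not written down beforehand, it will be either omitted or chosen after the data are seen.

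**Working it through.** **Step 1: does arm enter any analysis in Section 13?**

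| Aim | Analysis described | Arm term or contrast |
|---|---|---|
| 1 | Mean and median change against MCID; percentage reaching it | None |
| 1 | Generalized linear model of change on baseline | None |
| 1a | LOESS on duration; model rerun with duration | None |
| 1b | LOESS on step-target adherence; model rerun with adherence | None |
| 1c, 2 | Satisfaction; recruitment time and cost | None |
| 3 | Postoperative outcomes calculated or tabulated | None |
| Interim | Aim 1 change against MCID, every 10 patients | None |

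Control patients are not mentioned in Section 13. For Aim 1b, Section 10 defines step-target adherence for intervention patients only. Activity journals are kept in both arms, but Section 13 gives them no role. Adherence also arises after randomisation. The Aim 1b model therefore cannot include controls as written, and it does not re-estimate a randomised effect.

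**Step 2: what the planned quantities estimate.** Let c be mean change under control conditions and d the added effect of the prescription.

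- Intervention arm alone: c + d. The Aim 1a wording about time available for the intervention makes this the likelier reading.
- Both arms pooled 1:1: [c + (c + d)]/2 = c + d/2.
- Between-arm difference: (c + d) − c = d.

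The error can go either way. With c = +20 m and d = 0, both uncontrolled readings show +20 m for a null intervention. With c = −20 m and d = 41.6 m (the between-group difference that Section 5 cites from an earlier trial), the intervention-arm mean is 21.6 m and the pooled mean is −20 + 20.8 = 0.8 m.

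**Step 3: illustrative size.** The plan states no SD, no MCID value and no final success rule, so it has no figure to reproduce. The inputs below are assumptions: SD of 6MWD change 60 m (range 40 to 80 m), MCID 20 or 30 m, c from 10 to 30 m, and d = 0. One hundred per arm assumes that all 200 subjects in Section 24 are randomised; 200 per arm assumes all 400 in Section 25.

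P(mean change ≥ MCID) = 1 − Φ[(MCID − c)/(SD/√n)]. With SD 60 m and n = 100 the standard error is 6 m. For MCID 20 m and c = 10 m this is 1 − Φ(10/6) = 0.048.

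| Setting | c = 10 | c = 20 | c = 30 |
|---|---|---|---|
| SD 60, n = 100, MCID 20 | 0.048 | 0.500 | 0.952 |
| SD 60, n = 100, MCID 30 | 0.0004 | 0.048 | 0.500 |
| SD 60, n = 200, MCID 20 | 0.009 | 0.500 | 0.991 |
| SD 40, n = 100, MCID 20 | 0.006 | 0.500 | 0.994 |
| SD 80, n = 100, MCID 20 | 0.106 | 0.500 | 0.894 |

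For the between-arm difference, P(difference ≥ 20 m) = 1 − Φ[20/(SD√(2/100))]. This gives 0.0002, 0.009 and 0.0385 for SD 40, 60 and 80 m, and c does not enter.

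**Step 4: precision of the missing contrast.** The unadjusted 95% half-width is 1.96 × 60 × √(2/n per arm):

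- 100 per arm: 16.6 m
- 90 per arm (10% without a preoperative value): 17.5 m
- 80 per arm (20% without one): 18.6 m
- 200 per arm: 11.8 m

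At the interim looks, using t quantiles, it is 2.306 × 37.9 ≈ 87 m with 5 per arm. If looks are cumulative, it is 2.101 × 26.8 ≈ 56 m at 20 patients and 2.011 × 17.0 ≈ 34 m at 50.

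**The case against.** The strongest reply is that this is silence, not a wrong choice. Section 10 anticipates allowing for baseline differences between arms, and Aim 1b in Section 4 speaks of the effect of the intervention, so an arm term may have been intended. Section 13 would also permit tabulating change by arm. This is fair as to intent. But neither place gives a contrast, model, time point or population, and a table by arm still contains no estimate of the difference. Aim 1b speaks of re-estimating an effect that Section 13 never estimates in the first place.

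Four narrower points stand as qualifications.

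- The probabilities in Step 3 rest on assumed values and show only positive c. A negative c would hide benefit. They illustrate the problem; they are not false-positive rates of a stated rule.
- The Interim Analyses text allows the intervention to be revised along the way, so d would be an average over versions. With missing preoperative values, even the between-arm difference is not automatically free of bias.
- Section 11 does not say in so many words that controls attend the preoperative assessment, though that is the natural reading. Section 10 says gait speed was already measured at screening, while the screening in Section 11 describes only the frailty scale.
- An MCID applied to change within a patient is not automatically the yardstick for a difference between arm means.

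**Conclusion.** The concern holds and should be fixed before arms are compared. Section 13 contains no between-arm comparison for Aim 1 or for any other aim, and no stated role for control patients. That is established by the text alone. The consequence follows from the algebra without outside figures: the analyses as written estimate c + d or c + d/2, and the two differ from d by c and by c − d/2. How far this matters in metres depends on c, the SD and the MCID, none of which the documents give. Under the assumed values, the chance that a null prescription shows an MCID-sized mean change runs from almost nil to almost certain, depending on c alone.

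**What to change.** 1. **Aim 1, 6MWD and SPPB components.** Regress change at the preoperative assessment on randomised arm and baseline, in all randomised patients as assigned. Exclude the up to 15 non-randomised test patients described in Sections 11 and 30. Report the adjusted difference with a 95% confidence interval for each measure, and show the proportions reaching the MCID by arm. State how the MCID will be used to interpret a difference in means. Keep within-participant summaries, by arm, as descriptive.
2. **Time point and missing values.** Section 11 places the preoperative test on the day of preoperative testing in one paragraph and on the day of surgery in another. State which visit supplies the value, confirm that controls attend it, and clarify where baseline gait speed is recorded. Say how patients without a preoperative value are handled, since Section 24 expects cancellations and loss to follow-up.
3. **VR-12.** Section 11 lists it at baseline and six months, possibly within the physical status measurements repeated in hospital and at 30 days, but not preoperatively. Reconcile this, then apply the same model.
4. **Aims 1a and 1b.** State which arm or arms the duration analysis uses. Fit the adherence association within the intervention arm and label it non-randomised.
5. **Interim Analyses.** This text reuses the Aim 1 analysis. Align it with the revised Aim 1 and say whether looks are per batch or cumulative, given the half-widths in Step 4.

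For 6MWD and SPPB the cost is analysis-plan wording, provided the visit and gait-speed points are confirmed. A preoperative VR-12, if wanted, adds one 12-item questionnaire.
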